Existing treatment methods show insufficient effectiveness. Aminosalicylates are only modestly effective; glucocorticoids can cause unacceptable adverse events and do not provide a benefit as maintenance therapy. Tumor necrosis factor (TNF) antagonists, although efficacious, may predispose patients to infections and other serious adverse reactions [3, 4, 6-10, 12, 28, 29]. Besides, a considerable portion of patients do not respond to the treatment with TNF-antagonists (primary non-responders) or will lose response to such therapies over time (secondary loss of response). New biological treatment medication Vedolizumab (Entyvio®) is the first and only gut selective biologic approved medication indicated for the treatment of adult patients with moderate to severe UC and CD, who have had an inadequate response with, lost response to, or were intolerant to either non-biological therapy or a tumor necrosis factor-alpha (TNF α) antagonists [15, 16, 25, 26].

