15.2.4. Potential study biases

The study limitations are those inherent to uncontrolled observational studies. Taking into account observational and uncontrolled nature of the study, fully evaluating of non-biological /biological treatment effectiveness will not be available. However, data regarding in real-life practice will be gathered and analyzed. The inclusion criteria are those that used when administering non-biological /biological treatment in practice and therefore, the same criteria as those that would have been used if we had performed a similar prospective study. This type of experimental design should prevent selection bias that could occur when patient enrollment is related to the development of the outcome. In prospective observational study like this attrition bias is possible, however, in case of early leaving study last data will be gathered and effectiveness will be estimated, these cases will not be excluded from effectiveness analysis.

Details of the statistical analyses will be presented in the Statistical Analysis Plan.

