## 8 STATISTICAL DATA PROCESSING

### 8.1 Statistical methods

#### 8.1.1 General information

Statistical analysis will be conducted using the software package Microsoft R Open version 4.0.2 from Microsoft R Application Network (MRAN) (<https://mran.microsoft.com>). Exact version of the software will be determined at the time of first interim analysis and will remain unchanged throughout the study. Version control for the software and related R packages used for statistical data processing will be performed using the CRAN Time Machine from Microsoft (or the purpose of reproducibility, MRAN hosts daily snapshots of the CRAN R packages and R releases as far back as Sept. 17, 2014). Statistical analysis will take data type and scale for each parameter when describing and analyzing the data.

Quantitative data (both continuous and discrete, if applicable) will be presented using the following parameters:

- Number of non-missing observations (n);
- Arithmetic mean (M);
- Standard deviation (SD);
- 95% confidence interval for the mean (95% CI);
- Median (Me);
- 25th percentile;
- 75th percentile;
- Minimal value (min);
- Maximal value (max);

Qualitative data including binary and categorical variables will be presented as number of cases per category, frequency for the category (relative to the non-missing number of observations), as well as 95% exact binary confidence interval calculated using Clopper-Pearson method (binary data) or Goodman method (categorical data).

Time-to-event data will be presented as median, 25th and 75th percentiles as well as graphically as Kaplan-Meyer survival curves with log-log 95% confidence intervals.

No statistical tests are planned for the primary endpoint of this study as all outputs will be purely descriptive. However, 95% significance level will be applied for all confidence intervals calculated, and exploratory statistical analysis will be conducted to identify statistically significant associations between treatment patterns and outcomes.

Medical history, concomitant conditions and adverse events will be coded using the MedDRA dictionary. As version of MedDRA is updated every six months, the first interim analysis will be conducted using the most current MedDRA version, and all subsequent analyses, including the

Protocol ID	MACS-2017-102279	STATISTICAL ANALYSIS PLAN	Page 23 of 41	
IP	N/A		Date	30.12.2021
ID	MACS-2017-102279_SAP		Version	v1.2 final

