- Average maximum dose for each component of the combination (across all courses);
- Average number of courses per patient;
- Total duration of use of each combination / course for the total duration of observation (retro- and prospective);
- Distribution of each pattern by subgroups: age, gender, region, duration of the disease, disease activity (according to Visit 1 Mayo / Harvey-Bradshaw indices).

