### 8.3 Applicable significance level

Analysis will be performed in a descriptive manner, so, there will be no applicable statistical tests. However, 95% confidence intervals will be calculated for means and proportions, so, 95% significance level will be applied that corresponds to 5% alpha (type I) error.

As there are no statistical tests applied to any of the tabulated data, there will be no multiplicity (multiple comparison) corrections applied to the significance level.

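### SAP 8.1.1 plans a search for significant pattern–outcome associations that SAP 8.3 rules out; no adjustment is specified, so a crude search can report confounding by indication as a treatment association

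*SAP*

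**What the plan says.** SAP 8.1.1 first states: "No statistical tests are planned for the primary endpoint of this study as all outputs will be purely descriptive". It then adds that "exploratory statistical analysis will be conducted to identify statistically significant associations between treatment patterns and outcomes". It does not say which outcomes, which contrasts between patterns, which test or model, or which covariates.

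SAP 8.3 reads differently: "Analysis will be performed in a descriptive manner, so, there will be no applicable statistical tests". It keeps a 5% level for the intervals ("so, 95% significance level will be applied that corresponds to 5% alpha (type I) error") and uses the absence of tests to justify having no correction: "As there are no statistical tests applied to any of the tabulated data, there will be no multiplicity (multiple comparison) corrections applied".

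On how treatment is chosen, both documents say it follows routine practice. Protocol 5.1 describes vedolizumab as indicated for patients "who have had an inadequate response with, lost response to, or were intolerant to either non-biological therapy" or anti-TNF treatment. Protocol 15.2.4 concedes that "fully evaluating of non-biological /biological treatment effectiveness will not be available", and Protocol 10.3 relies on subgroup analysis to deal with heterogeneity.

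SAP 7.4 lists subgroups by activity at prescription, steroid courses, time since diagnosis, line of therapy, response to immunosuppressives and surgery. SAP 8.1.4 makes their use optional. SAP 8.1.2 plans "Distribution of each pattern by subgroups: age, gender, region, duration of the disease, disease activity" at Visit 1. That shows who receives which pattern, not how outcomes compare between similar patients.

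**The concern.** Patients who reach a biologic, or a second biologic, tend to do so because something else failed. If earlier failure or severity also predicts later failure, patterns will differ in outcome even when the drugs do not differ in effect. No correction for multiple testing removes this, because a single unadjusted comparison is already biased.

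A p-value below 0.05 attached to a pattern invites an effectiveness reading, which Protocol 15.2.4 says the study cannot fully support. The descriptive primary endpoint is not affected. What is at stake is how comparative statements on failure or remission between patterns are read.

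**Working it through.** **1. Do the existing strata cover the gap?**
- The HBI and partial Mayo strata in SAP 7.4 appear only under the four first-line drugs. None is listed for patients not assigned to biologics, so they cannot balance biologic against non-biologic patterns.
- For patients not assigned to biologics, the steroid-course and time-since-diagnosis strata are still anchored to the prescription of a biologic. Patients never prescribed one have no such date.
- Response to immunosuppressives, line of therapy and surgery are single-factor descriptive splits that nothing links to the association search.
- The outcome tables in SAP 8.1.3 are built on the first combination recorded in the two-year retrospective window. The visit schedule collects disease activity data only from Visit 1, so activity at the start of an older treatment may not be available.
- Neither document mentions regression, propensity scores, weighting, matching or a pooled stratified estimate. The example tables in SAP section 9 were not available for this check.

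**2. The plan's own figure.** Protocol 15.4 assumes 2000 patients, 40% CD, 40% on biologics and 10% drop-out: 2000 × 0.4 × 0.4 × 0.9 = 288. The half-width at 50% failure is 1.96 × √(0.5 × 0.5 / 288) = 5.77 points, which matches the stated ±5.8. SAP 8.2 still uses 3000, but a footnote in SAP 8.7 says 2000, so 2000 is used here. The sizing is for precision; no comparison between patterns is powered.

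**3. Illustration with no true treatment effect.** Analysed numbers from the same assumptions:
- CD: 288 on biologics, 432 not.
- UC: 432 on biologics, 648 not.

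The documents give neither the severity split nor its effect on failure, so these are assumptions. Half the patients are more severe, and 12-month failure is 55% in them and 35% in the rest.

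*Scenario A:* biologics go to 60% of the more severe and 20% of the less severe (40% overall).
- More severe share on biologics: 0.30/0.40 = 75%; not on biologics: 0.20/0.60 = 33.3%.
- Failure on biologics: 0.75 × 0.55 + 0.25 × 0.35 = 50.0%.
- Failure not on biologics: 0.333 × 0.55 + 0.667 × 0.35 = 41.7%.
- False difference d: 8.3 points.

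*Scenario B:* biologics go to 50% and 30% (40% overall).
- More severe share: 0.25/0.40 = 62.5% and 0.25/0.60 = 41.7%.
- Failure: 47.5% and 43.3%.
- False difference d: 4.2 points.

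With SE = √(p₁(1−p₁)/n₁ + p₀(1−p₀)/n₀), the chance of p < 0.05 is Φ(d/SE − 1.96) + Φ(−d/SE − 1.96):

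| | CD: d/SE | CD: P(p<0.05) | UC: d/SE | UC: P(p<0.05) |
|---|---|---|---|---|
| A | 0.0833/0.0378 = 2.20 | 0.60 | 0.0833/0.0309 = 2.70 | 0.77 |
| B | 0.0417/0.0379 = 1.10 | 0.20 | 0.0417/0.0309 = 1.35 | 0.27 |

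**4. How far this moves.**
- *Small patterns.* SAP 8.1.2 allows combinations seen in fewer than 25 subjects to be dropped. For two patterns of 50 each, A gives 0.13 and B 0.07. For 25 each, they give 0.09 and 0.06.
- *Small imbalance.* If the confounder is present in 50% versus 40% of the groups and failure is 50% versus 40%, the false difference is 1 point and the crude test is significant about 6% of the time in both diseases.
- *Stratifying.* In 20,000 simulated studies per scenario, over a grid of imbalances that included this one, a Mantel-Haenszel test stratified on the confounder stayed at about 5% throughout.

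**The case against.** The best defence is that the plan is descriptive, the sentence is labelled exploratory, SAP 8.3 says nothing is tested, and the protocol disclaims a full evaluation of effectiveness. SAP 8.1.1 also does not say that the search will be unadjusted. All of this is true. A reader might infer that confounded results will certainly be published as treatment effects. The documents do not support that; they support only that this can happen if the plan is followed as written. The disclaimers also do not cancel a stated aim of finding significance, and 8.3 contradicts that aim without withdrawing it.

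A reader might also infer that the SAP ignores severity and prior failure. It does not. SAP 7.4 crosses first-line drugs with activity, steroid courses and time since diagnosis, and SAP 8.1.3 lists disease severity, complications and surgery among the T2T factors. What stands is narrower: no adjustment is specified for the association search, and the strata do not reach the biologic versus non-biologic contrast.

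A third tempting step is to quote a near-certain false finding. Widening the failure gradient in scenario A to 60% versus 30% gives 0.91 in CD and 0.98 in UC. But that implies 52.5% failure on biologics, above the plan's own 40–50%. Every patient must also have had a moderate to severe flare, so the true severity gap is unknown. Nor is a two-group split the same as a comparison among 17 listed combinations.

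**Conclusion.** The point holds as a conflict between two SAP sections plus an unaddressed risk. SAP 8.1.1 commits to looking for significant associations, SAP 8.3 denies any testing, and no adjustment is specified although treatment choice depends partly on earlier failure.

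The probabilities of 0.20–0.60 in CD and 0.27–0.77 in UC illustrate size and do not predict what the study will show. They rest on the plan's group sizes, a two-sided 5% test, a single binary confounder with assumed gradients, and a crude biologic versus non-biologic contrast. They fall towards 5% with small patterns or little imbalance.

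The sponsor should correct this before comparative results are reported.

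**What to change.** **Preferred.** Delete the significance-search sentence so that 8.1.1 agrees with 8.3, and report outcomes by pattern descriptively with 95% confidence intervals. This costs one line of text.

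**If the analysis is kept**, amend 8.3 and define it separately for UC and CD:
- Use broad treatment class as the exposure, a stated time zero, and a named outcome after it. If time zero is Visit 1, say that this departs from the original-combination exposure in SAP 8.1.3.
- Give crude and adjusted estimates with 95% confidence intervals.
- Adjust for covariates that precede the exposure: disease duration, extent or location, prior biologic and number of prior therapies, prior steroid courses, age, and country or site.
- Do not adjust for steroid use where it is part of the pattern, as it is in several SAP 8.1.2 combinations.
- Adjust for Visit 1 HBI or partial Mayo only for treatments started at or after Visit 1, or as a sensitivity analysis. Eligibility requires current treatment, so for ongoing users the score is measured on treatment and may be a consequence of it.
- State how missing covariates and multiplicity are handled, and label the results as associations, not effectiveness.

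This needs no new data. The costs are patients lost to missing covariates, probably few new starters at or after Visit 1, and residual confounding that the report must state.

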#### 8.1.2 Assessment of primary endpoint

Treatment combinations will be described for UC and CD separately based on the following criteria:

- 1) Various types of biological and non-biological treatments including the following treatment combinations:
  - a. Steroid monotherapy (by class)
  - b. Steroids (by class) + immunosuppressive therapy (by class) combinations
  - c. Immunosuppressive monotherapy (by class)
  - d. Immunosuppressive (by class) + 5-aminosalicylic acid derivatives (by class)
  - e. 5-aminosalicylic acid derivatives monotherapy (by class)
  - f. TNF-alpha inhibitor monotherapy (by trade name)
  - g. TNF-alpha inhibitor therapy (by trade name) + steroids (by class)
  - h. TNF-alpha inhibitor therapy (by trade name) + immunosuppressive therapy (by class)
  - i. TNF-alpha inhibitor therapy (by trade name) + immunosuppressive therapy (by class) + steroids (by class)
  - j. Vedolizumab monotherapy (by INN)
  - k. Vedolizumab therapy (by INN) + immunosuppressive therapy (by class)
  - l. Vedolizumab therapy (by INN) + steroids (by class)
  - m. Vedolizumab therapy (by INN) + immunosuppressive therapy (by class) + steroids (by class)
  - n. Janus kinase (JAK) inhibitor monotherapy (by trade name)
  - o. JAK inhibitor therapy (by trade name) + steroids (by class)
  - p. JAK inhibitor therapy (by trade name) + immunosuppressive therapy (by class)
  - q. JAK inhibitor therapy (by trade name) + immunosuppressive therapy (by class) + steroids (by class)

---

 Steroids will be standardized through the calculation of prednisolone equivalent dose to facilitate comparisons between the classes

Protocol ID	MACS-2017-102279	STATISTICAL ANALYSIS PLAN	Page 24 of 41	
IP	N/A		Date	30.12.2021
ID	MACS-2017-102279_SAP		Version	v1.2 final

**Disclaimer:** due to the observational nature of the study, it is impossible to predict the distribution of treatment patterns before the actual analysis is performed. The list above can be modified based on the actual study data by excluding of certain combinations (absent in the database or identified in less than 25 subjects) or by including the combinations that were not initially planned but were identified in the actual study database.

Treatment pattern will include unique combination of certain treatments or treatment combinations along with their change over time.

Each treatment combination will be analyzed using the following summary data:

- Average course duration;
- Average maximum dose for each component of the combination (across all courses);
- Average number of courses per patient;
- Total duration of use of each combination / course for the total duration of observation (retro- and prospective);
- Distribution of each pattern by subgroups: age, gender, region, duration of the disease, disease activity (according to Visit 1 Mayo / Harvey-Bradshaw indices).

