Augmentation with non-biological therapy will be defined as starting a new non-biological drug or increase in dose/frequency of the concurrent non-biological drugs with biological therapy. Non-biological therapies included aminosalicylates, immunomodulators, and corticosteroids;

Switching will be defined as a subset of initial biologic agent discontinuers who initiated another biological therapy;

IBD-related surgery will include but not be restricted to colectomy, ostomy (colostomy or ileostomy), fistula repair, abscess repair, and strictureplasty.

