**Subgroups depending on the use of drugs in the first- and second-line therapy**

- a. Ustekinumab in the first line, vedolizumab in the second line
- b. Ustekinumab in the first line, anti-TNF- $\alpha$  in the second line
- c. Ustekinumab in the first line, tofacitinib in the second line
- d. Vedolizumab in the first line, tofacitinib in the second line
- e. Vedolizumab in the first line, ustekinumab in the second line
- f. Vedolizumab in the first line, anti-TNF- $\alpha$  in the second line
- g. Anti-TNF- $\alpha$  in the first line, ustekinumab in the second line
- h. Anti-TNF- $\alpha$  in the first line, vedolizumab in the second line
- i. Anti-TNF- $\alpha$  in the first line, tofacitinib in the second line
- j. Tofacitinib in the first line, ustekinumab in the second line
- k. Tofacitinib in the first line, anti-TNF- $\alpha$  in the second line
- l. Tofacitinib in the first line, vedolizumab in the second line

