#### 8.1.3 Assessment of secondary and exploratory endpoints

**Each original treatment combination** (defined as the treatment combination that was used by the patient at the very start of retrospective observation period, i.e. first recorded treatment combination in the study) will be tabulated by the below listed parameters using the generic table format below (see example tables: Table 10, Table 11, Table 12 and Table 6):

- Demographic data;
- Disease activity at Visits 1, 2, 3 (Mayo, Harvey-Bradshaw indices);
- Disease status assessed by investigator at Visits 1, 2, 3;
- Frequency (percentage) of clinical, endoscopic and histologic remission at Visits 1, 2, 3 and retrospective period of observation;
- Extent of lesion at Visits 1, 2, 3;
- Systemic (extraintestinal) manifestations at Visits 1, 2, 3;
- Total number, duration and severity of disease exacerbations by Visit 1, 2 and 3;
- Total number, type and duration of disease complications by Visit 1, 2 and 3;
- Laboratory and instrumental assessments at Visits 1, 2, 3;
- Percentage of patient with surgical treatment by Visits 1, 2, 3 grouped by:
  - Indication;
  - Surgery type;
  - Presence of complications.
- Number of surgeries by Visits 1, 2, 3;

Protocol ID	MACS-2017-102279	STATISTICAL ANALYSIS PLAN	Page 25 of 41	
IP	N/A		Date	30.12.2021
ID	MACS-2017-102279_SAP		Version	v1.2 final

- Percentage of patients with at least one episode of failure or biological or/and non-biological therapy (e.g., dose escalation of biologics, switching to another therapy, IBD-related surgery, medication augmentation) by Visits 1, 2 and 3;
- Separately for patients who achieved / not achieved T2T treatment goals (based on the clinical assessment of IBD) by Visits 1, 2 and 3:
  - Presence of therapeutic de-escalation;
  - Presence of therapeutic escalation;
  - Continuation of therapy without any changes.
- Healthcare resources utilization:
  - Hospitalizations due to complications;
  - IBD-related surgeries;
  - Percentage of patients that used healthcare resources;
- Only for biological therapy - percentage (by Visits 1, 2, 3) of patients with:
  - Positive test results for TB before the start of biological therapy;
  - Active TB before the start of biological therapy;
- Percentage of patients by Visits 1, 2, 3 with:
  - Reactivation of TB;
  - New occurrence of TB.

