**The same information will be provided for the treatment pattern (if the corresponding treatment pattern will be large enough to make statistical inferences).**

As treatment pattern change over time, patterns will be assessed for certain time points and the change of patterns will be tracked throughout the study (see also example Table 8):

- Retrospective treatment pattern (change assessment for every 6 months of the 2-year treatment interval);
- Treatment pattern between the date of enrollment and 6 months;
- Treatment pattern between 6 and 12 months.

Accordingly, for each above-mentioned period, each pattern will be assessed for the history of changes (see example Table 8):

- Presence of dose modifications;
- Presence of discontinuations / treatment changes;
- Presence of flares (during the course of treatment);
- Add-on therapy.

Protocol ID	MACS-2017-102279	STATISTICAL ANALYSIS PLAN	Page 26 of 41	
IP	N/A		Date	30.12.2021
ID	MACS-2017-102279_SAP		Version	v1.2 final

In order to track the history of transition of subject “states” (i.e. treatment using the certain pattern from the list above), in addition to the descriptive 6-monthly data, transition state (Sankey) diagrams will be built (see Figure 2 for mock example) to visualize the subject journey across patterns as well as trends of pattern change over time.

Treat-to-target (T2T) success will be assessed (in this SAP) using EDC data, based on the definition of failure to meet T2T goals (*lack of clinical and endoscopic remission based on investigator's feedback and objective methods of evaluation*). Overall T2T success or failure will be analyzed separately from this SAP using Investigator Survey data.

T2T treatment factors will be assessed by Visits 1, 2 and 3 and will be grouped by:

- Clinician-related factors:
  - Frequency and methods of assessment of UC/CD disease activity;
- Patient-related factors:
  - Demographic data;
  - Time frame between the date of first symptom(s) and the date of IBD diagnosis;
  - Smoking status;
- Disease-related factors:
  - Age of disease onset;
  - Location of disease;
  - Clinical course;
  - Disease severity;
  - Presence of intestinal and systemic (extraintestinal) manifestations;
  - Presence of complications;
  - Surgical treatment.

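### Failure and treatment-change rates are tabulated by treatment patterns that already contain those changes, so any whole-period pattern with a biologic switch or add-on shows 100% failure by construction

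*SAP*

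**What the plan says.** SAP 8.1.2 lists combinations a to q and then defines the pattern: "Treatment pattern will include unique combination of certain treatments or treatment combinations along with their change over time".

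SAP 8.1.3 sets out a long list of table rows. One is the percentage of patients with treatment failure, defined by examples: "e.g., dose escalation of biologics, switching to another therapy, IBD-related surgery, medication augmentation) by Visits 1, 2 and 3". Others are therapeutic escalation, de-escalation and unchanged therapy, split by whether T2T goals were met. These rows are first tabulated by the original combination, "defined as the treatment combination that was used by the patient at the very start of retrospective observation period". The SAP then adds: "The same information will be provided for the treatment pattern", on condition that the pattern is large enough. SAP 8.1.4 gives every summary table a column per pattern, as does Protocol 15.2.1.

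Protocol 4.2 defines the failure components. On switching: "Switching will be defined as a subset of initial biologic agent discontinuers who initiated another biological therapy". Augmentation is a new non-biological drug, or more of a concurrent one, given with a biologic. Dose escalation is any increase in a biologic's dose or frequency.

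Two further places build on patterns or sequences. SAP 8.1.1 says "exploratory statistical analysis will be conducted to identify statistically significant associations between treatment patterns and outcomes". SAP 7.4 adds 12 first- and second-line sequences, for example "Ustekinumab in the first line, vedolizumab in the second line".

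**The concern.** A pattern that includes its own changes is known only after those changes have happened. If the change is also the outcome, the column heading determines the row. A patient can enter a column that contains a biologic switch only by switching, and switching counts as failure. The treatment-action rows have the same problem: they largely restate whether the pattern contains a change.

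Failure matters here. Protocol 15.4 and SAP 8.2 call it a key secondary objective and size the study on it. Failure percentages by pattern, printed with exact 95% intervals, would invite comparison between drugs. Much of the contrast would come from the grouping rule, and the association analysis in SAP 8.1.1 could report it as a finding.

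**Working it through.** **1. The plan's own figures.** Inputs from Protocol 15.4 and SAP 8.2: 40% of patients on biologics, about 40% with CD, 10% drop-out, and a failure rate of 40–50% over 12 months. With a total of 2000, n = 2000 × 0.40 × 0.40 × 0.90 = 288. The half-width is 1.96 × √(p(1−p)/n):
- p = 0.50: 5.77 points, giving 44.2–55.8%
- p = 0.40: 5.66 points, giving 34.3–45.7%

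Both match the printed table. The SAP text uses a total of 3000, so n = 432 and the half-width at 50% is 4.71 points, which also matches. These figures concern all CD patients on biologics together. They do not depend on patterns and are not affected.

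**2. Which changes force failure.**

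| Event | Changes the listed combination (a to q)? | Listed as failure? |
|---|---|---|
| Switch from one biologic to another | Yes, where the two fall in different listed combinations | Yes |
| Immunosuppressant or steroid added to a biologic | Yes | Yes (augmentation) |
| Biologic dose or frequency increased | No, but SAP 6.1 counts dosage regimen and modifications as part of the pattern | Yes |
| IBD-related surgery | No | Yes |
| Steroid stopped, or therapy de-escalated | Stopping a drug does; a dose reduction does not | No |

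The first two rows give 100% failure once the event falls within the period counted. The third is unclear in the SAP. The fourth means an unchanged pattern can still include failures. The fifth means a changed pattern need not be at 100%.

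**3. Size.** Let f be the overall failure rate, equal for all drugs. Let s be the share of failing patients whose failure includes a switch or an added drug. The documents do not give s, so a range is shown. Patients whose pattern contains such an event make up f·s of the total, and all of them fail. The pooled rate in everyone else is (f − f·s)/(1 − f·s).

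| s | Patients of 288 at 100%, f = 40% | Rate in the rest, f = 40% | Rate in the rest, f = 50% |
|---|---|---|---|
| 0.25 | 29 | 0.30/0.90 = 33.3% | 0.375/0.875 = 42.9% |
| 0.50 | 58 | 0.20/0.80 = 25.0% | 0.25/0.75 = 33.3% |
| 0.75 | 86 | 0.10/0.70 = 14.3% | 0.125/0.625 = 20.0% |
| 1.00 | 115 | 0/0.60 = 0% | 0/0.50 = 0% |

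At f = 40% the apparent gap runs from 100 − 33.3 = 66.7 points to 100 points, although no drug differs from any other.

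**4. How it would look in print.** SAP 8.1.2 allows a combination seen in fewer than 25 patients to be dropped. In a pattern of 25 patients all defined by a switch, the Clopper–Pearson interval for 25/25 has lower limit 0.025^(1/25) = 86.3%. The table would show 86.3–100%, an apparently precise estimate of something true by definition.

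**5. Tables without the problem.** The original combination is fixed at the start of the retrospective period, before any recorded change. Under equal drug effects, each of its columns would have expected failure rate f.

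**The case against.** The strongest counter-argument is that the SAP uses the word pattern in two ways. In SAP 8.1.3 patterns are also assessed in six-month windows, and the Sankey text treats a pattern as a state from the listed combinations. The same section checks each pattern for treatment changes and add-on therapy, which would be redundant if those changes already defined it. On that reading the column is not the outcome. This stands as an ambiguity but does not settle the matter. The explicit definition in 8.1.2 includes change over time, the SAP does not say which version feeds the failure table, and nothing requires the pattern to be fixed before failure is counted.

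Other mitigating points hold. The first-named failure table is by original combination and is sound. The pattern version is conditional on size. SAP 8.3 says no tests apply, and SAP 8.1.1 names neither a test nor failure as an outcome, so a significant pattern–failure association is possible but not stated. Protocol 15.2.4 disclaims full evaluation of effectiveness.

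A reader might infer that every by-pattern rate is fixed at 100% or 0%, or that an unchanged pattern can fail only through surgery. The documents do not support this. Stopping a steroid changes a pattern without being a listed failure, whether dose escalation changes a pattern is unclear, and the failure list consists of examples. A reader might also infer that the 12 sequences in SAP 7.4 will be reported with 100% failure. No failure table is specified for them: SAP 8.1.4 says only that data can be divided by these subgroups.

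**Conclusion.** The point holds for whole-period patterns. Where such a pattern contains a biologic switch or a drug added to a biologic, failure is 100% by construction. In the remaining patterns it is biased downwards but not determined. At a common 40% failure rate, the remaining patients would show between 33% and 0% for shares of 25% to 100%. This assumes equal drug effects, a pattern period that covers the counting period, and a share that the documents do not supply. The escalation, de-escalation and no-change rows are affected in the same way.

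The conclusion does not extend to the original-combination table, the overall UC and CD failure proportions, or their stated precision. Nor does it mean that the study's failure analysis as a whole is uninformative.

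**What to change.** In SAP 8.1.3:
- Keep the original-combination table unchanged.
- For the pattern version, report the failure and treatment-action rows only by the combination in force at the start of each risk window, and count only events after that point. The starting points are the start of each retrospective six-month window, V1 for V1–V2 and V1–V3, and V2 for V2–V3.
- Keep whole-period patterns and Sankey diagrams as description, without those rows.
- Leave the remission, surgery and retrospective tables as planned. Limiting them to V1 and V2 columns would lose retrospective results that Protocol 6.2 and SAP 8.1.3 require.

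In SAP 7.4, if failure is reported for the first- and second-line sequences, count only failures after the second-line start date.

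In SAP 8.1.1, exclude failure and treatment-action outcomes by whole-period pattern from the exploratory association analysis.

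The cost is SAP wording, some table reprogramming and fewer rows in the whole-period pattern tables. Protocol 12.6.1 already collects treatment start and end dates, so no new data are needed.
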